#### 3.1.3 Dose Escalation

The original plan was to treat up to 10 participants at the 40 mcg/kg dose level, up to 16 total participants could have been required (including up to 10 participants at the 30 mcg/kg dose level) if there were 2 DLTs within the first 6 participants treated at the 40 mcg/kg dose. The accrual ceiling was set at 20 participants considering screen failures and/or inevaluable participants. Please refer to Section 10.2 for dose-escalation rules and below.

Initially, 3 participants were to be treated with moxetumomab pasudotox-tdfk 30 mcg/kg and rituximab 375 mg/m^2. If 0/3 had a DLT, then the next 3 participants would be treated with moxetumomab pasudotox-tdfk 40 mg/kg and rituximab 375 mg/m^2.

[figure not shown]
If 1/3 initial participants treated with 30 mcg/kg had a DLT, then 3 more would have been treated at 30 mcg/kg. If no more than 1 of the first 6 had a DLT, then 4 more participants were to have been enrolled at 30 mcg/kg provided that no more than a total of 2 of the 10 at the 30 mcg/kg level would have a DLT.

If participants were accrued to the 40mcg/kg level, if 0/3 or 1/3 had a DLT, then 3 more were to be treated using those dose levels. If no more than 1 of the first 6 had a DLT, then 4 more participants were to be enrolled provided that no more than 2 total of the 10 at the 40 mcg/kg level had a DLT with the exception of the types noted. If a 3rd participant had a DLT, accrual would end as soon as this is noted.

If 2 of the first 3 participants, or 2 of the first 6 participants, treated with moxetumomab pasudotox-tdfk 40 mcg/kg and rituximab 375 mg/m² had a DLT, then 3 additional participants were to be treated with moxetumomab pasudotox-tdfk 30 mcg/kg and rituximab 375 mg/m². If 0/3 or 1/3 of these next 3 had a DLT with these dose levels, then 4 more participants were to be enrolled at the 30 mcg/kg level provided that no more than 2 total of the 10 at the 30 mcg/kg level had a DLT. If 2 participants in the first 6 had a DLT at this level, then the trial would have ended accrual.

Furthermore, at any time in the 10 participants, if a 3rd participant had a DLT, accrual will also end as soon as that was noted.

## 3.1.3.1 Dose Escalation Schema

Though DLT will be evaluated for the duration of study therapy, the 4th and 7th evaluable participants could be enrolled after a minimum of 30 days after the previous participant received the last dose of cycle 2 or last dose of cycle 1 if the participant was not to receive a 2nd cycle.

Dose Escalation Schedule						
Dose Level Dose of IND Agent *						
Level 1	Moxetumomab pasudotox-tdfk 30 mcg/kg					
Level 2	Moxetumomab pasudotox-tdfk 40 mcg/kg					

## 3.1.4 Dose Expansion

As of 9/24/21, 12 participants were enrolled, 3 that received moxetumomab pasudotox-tdfk at 30 mcg/Kg and 9 at 40 mcg/Kg. All participants were without DLT, therefore per protocol only 1 additional eligible participant treated with moxetumomab pasudotox-tdfk at 40 mcg/Kg could be enrolled, making a total of 13 eligible participants. After these participants, to better determine safety and efficacy, an additional 13 eligible participants will be enrolled and treated with moxetumomab pasudotox-tdfk at 40 mcg/Kg in combination with Ruxience instead of rituximab.

#### 3.2 DRUG ADMINISTRATION

## 3.2.1 Moxetumomab pasudotox-tdfk

Moxetumomab pasudotox-tdfk is administered at 30-40 mcg/kg intravenous (IV) over 30 min using early call back/reverse flow method (intended dose level 1). Moxetumomab pasudotox-tdfk is given on days 1, 3, and 5 of each cycle. When given on the same day as a rituximab/Ruxience infusion, the rituximab/Ruxience will be given first followed by Moxetumomab pasudotox-tdfk. Participants will receive up to 4 cycles past documentation of CR without MRD, maximum 8. To prevent renal toxicity and hypovolemia, participants will be encouraged to drink water gradually, approximately 1 cup/hour or 6L/day, and to avoid going >3 hours without drinking from days 1 to 8. To prevent rituximab/Ruxience toxicity, participants will receive prophylactic dexamethasone as indicated in Section 3.2.3, before the 1st dose of rituximab/Ruxience, and before subsequent doses until rituximab/Ruxience infusion reactions are not seen. Diphenhydramine, famotidine, and acetaminophen may be used as needed. Dexamethasone 4 mg orally (maximum 2 doses/24 hours) will be given to treat nausea or fever associated with moxetumomab pasudotox-tdfk, which otherwise might prevent adequate water intake.

Please refer to Appendix C for information related to moxetumomab pasudotox-tdfk administration and preparation. Handle moxetumomab pasudotox-tdfk with caution to avoid skin and mucus membrane contact, aerosol formation, or ingestion. Monitor participants for infusion reactions, CLS, TLS, and thrombotic microangiopathy/HUS. To monitor for HUS, before every infusion, hemoglobin levels, platelet count, and serum creatinine will be checked. If HUS is suspected, blood LDH, indirect bilirubin, blood smear schistocytes for evidence of hemolysis will be promptly checked. Appropriate supportive measures will be taken, including fluid repletion and hemodynamic monitoring. Hospitalization should be considered if clinically indicated. If participants develop HUS, moxetumomab pasudotox-tdfk will be discontinued. To monitor for CLS, it is recommended that before every infusion, participants' weight and blood pressure are checked. CLS will be considered if participant's weight has increased by 5.5 pounds (2.5 kg) or ≥5% from day 1 of each cycle and the participant is hypotensive. Peripheral edema, hypoalbuminemia, and respiratory symptoms, including shortness of breath and cough, will be checked. If CLS is suspected, decrease in oxygen saturation, evidence of pulmonary edema, and/or serosal effusions will be checked. Appropriate supportive measures, including administration of concomitant corticosteroids PO or IV, will be used. Hospitalization will be considered if clinically indicated.

Vital signs will be obtained every 15 ( $\pm$  10) minutes during the moxetumomab pasudotox-tdfk infusion, then every hour ( $\pm$ 30 minutes) for an additional 4 hours during Cycle 1. During subsequent cycles, vital signs will be obtained as indicated in the **Study Calendar**. Weight, CBC + Diff, chemistries and urinalysis will be assessed prior to each infusion of moxetumomab pasudotox-tdfk.

To mitigate risk for allergic reaction and fever, participants will be premedicated with acetaminophen and famotidine, as indicated in Section 3.2.3. Substitutions of cimetidine for famotidine is permitted. In participants experiencing infusion-related reactions, including, but not limited to pyrexia, nausea, or dyspnea, premedication with dexamethasone and/or diphenhydramine intravenous (IV) or oral may be administered at the investigator's discretion as secondary prophylaxis.

Version Date: 04/16/2025

In an attempt to prevent renal insufficiency, participants will receive fluid and aspirin prophylaxis. Participants will receive low-dose aspirin orally (81 mg daily or local standard dose) on Days 1-8 of those cycles with platelet counts  $\geq 100 \times 10^9$ /L. Aspirin will be held on days where the platelet count is below 75 x 10^9/L. Participants will be hydrated (recommended over 2-4 hours) prior to the beginning of each moxetumomab pasudotox-tdfk infusion, as indicated in Section 3.2.3. Diuresis should be considered for a > 10% increase in weight above baseline and may be most safely given during the pre-hydration liter of fluid. Participants will be encouraged to measure and record their weight daily, as well as their fluid intake during days 1-8. Participants will be provided with a hydration diary (see Appendix D: Participant Hydration Diary), instructed in its use, and asked to bring the diary with them at each appointment. Participants with hyperuricemia of > 10 mg/dL (> 0.59 mmol/L) prior to administration of moxetumomab pasudotox-tdfk will receive allopurinol 300 mg once daily for tumor lysis syndrome (TLS) prophylaxis. Treatment of TLS will be based on institutional guidelines. Adequate Pneumocystis carinii pneumonia (PCP) prophylaxis will be considered for participants receiving > 1 week of corticosteroids  $\ge 10$  mg of prednisone daily or equivalent and CD4 lymphocyte count  $< 0.2 \times 10^9 / L$ , or at the discretion of the investigator. Viral prophylaxis will be also considered for participants receiving chronic corticosteroids or with lymphopenia. Participants should not receive non-steroidal anti-inflammatory medications (NSAIDS), other than aspirin for prophylaxis of renal insufficiency, during the course of the study through 7 days after the last dose of moxetumomab pasudotox-tdfk. An event of  $\geq$  Grade 2 hypercalcemia with calcium level corrected for serum albumin will require a delay in dosing until resolution to < Grade 2. If visual symptoms  $\geq$  Grade 2 are reported, an ophthalmologic examination including slitlamp and fundoscopic evaluation is required. If a > 10% increase in body weight due to fluid overload occurs, it is recommended that imaging of the chest is obtained for any evidence of pulmonary edema so appropriate treatment may be instituted promptly.

Please refer to the proper prescribing information for full details regarding toxicity as this agent has recently been FDA approved.

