#### 2 ELIGIBILITY ASSESSMENT AND ENROLLMENT

#### 2.1 ELIGIBILITY CRITERIA

#### 2.1.1 Inclusion Criteria

- 2.1.1.1 Diagnosis of HCL or HCLv.
- 2.1.1.2 Treatment required for either 1) Absolute neutrophil count (ANC) <1/nL, 2) Hemoglobin <10g/dL, 3) Platelets<100/nL, 4) symptomatic splenomegaly, or 5) enlarging HCL mass > 2cm in short axis. Participants who have eligible blood counts within 4 weeks from the initiation of study will not be considered ineligible if subsequent blood counts prior to enrollment fluctuate and become ineligible up until the time of enrollment.
- 2.1.1.3 Participants must be Pseudomonas-immunotoxin naïve.
- 2.1.1.4 HCL or HCLv with at least 1 prior purine analog, and, for HCL participants with ≥2-years 1 month response, at least 1 other therapy.
- 2.1.1.5 Age ≥18 years as the disease under study, HCL/HCLv, has not been reported in children < age 18.
- 2.1.1.6 ECOG performance status ≤2 (Karnofsky ≥60%, see **Appendix A: Performance Status** Criteria).
- 2.1.1.7 Participants must have adequate organ and marrow function as defined below:
  - Total bilirubin ≤ 1.5 mg/dL, unless consistent with Gilbert's (ratio between total and direct bilirubin > 5)
  - AST and ALT  $\leq$  3x upper limit of normal (ULN)
  - Alkaline phosphatase < 2.5 ULN
  - Serum creatinine  $\leq 1.5 \text{ mg/dL}$  or creatinine clearance  $\geq 60 \text{ mL/min}$  by Cockcroft-Gault equation, where creatinine clearance = (140 -age)(kg weight)/(72 x Creatinine)
  - Serum albumin > 2 g/dL
  - Partial thromboplastin time (PTT) or Prothrombin time (PT)/International Normalized Ratio < 2.5x ULN (If on warfarin, PT/INR < 3.5x ULN; If on any other anticoagulation, Prothrombin time (PT) < 2.5x baseline)
  - Fibrinogen  $\geq 0.5$  lower limit of normal
- 2.1.1.8 The effects of moxetumomab pasudotox-tdfk and rituximab/Ruxience on the developing human fetus are unknown therefore participants must use effective methods of contraception as directed below.

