## 2.1.2 Exclusion Criteria

- 2.1.2.1 Participants who have had chemotherapy, immunotherapy or radiotherapy within 4 weeks or treatment with rituximab/Ruxience within last 3 months prior to initiation of treatment.
- 2.1.2.2 Participants who are receiving any other investigational agents.
- 2.1.2.3 Breastfeeding within the projected duration of the study, starting with the screening visit through 6 months after the last dose of rituximab/Ruxience. Pregnant women are excluded from this study because moxetumomab pasudotox-tdfk and rituximab/Ruxience are agents with the potential for teratogenic or abortifacient effects. Because there is an unknown but potential risk for adverse events in nursing infants secondary to treatment of the mother with moxetumomab pasudotox-tdfk and rituximab/Ruxience, breastfeeding should be discontinued if the mother is treated with moxetumomab pasudotox-tdfk and rituximab/Ruxience.
- 2.1.2.4 Participants with known brain metastases should be excluded from this clinical trial because of their poor prognosis and because they often develop progressive neurologic dysfunction that would confound the evaluation of neurologic and other adverse events.
- 2.1.2.5 Uncontrolled intercurrent illness including, but not limited to, ongoing or active infection, symptomatic congestive heart failure, unstable angina pectoris, cardiac arrhythmia, uncontrolled hypertension, uncontrolled pulmonary infection, pulmonary edema or psychiatric illness/social situations that would limit compliance with study requirements.
- 2.1.2.6 Participants with retinal or choroidal detachment.
- 2.1.2.7 Positive for Hepatitis B core antibody or surface antigen unless the participant is on Tenofovir or Entecavir and Hepatitis B Viral deoxyribonucleic acid (DNA) load is <2000 IU/mL
- 2.1.2.8 Active second malignancy requiring treatment other than minor resection of indolent

cancers like basal cell and squamous skin cancers.

- 2.1.2.9 Human immunodeficiency virus (HIV)-positive participants unless taking appropriate anti-HIV medications with a CD4 count of > 200. Otherwise, there may be an increased risk of lethal infections when temporarily suppressing normal B-cells.
- 2.1.2.10 History of an allogeneic bone marrow transplant.
- 2.1.2.11 Participants with a history of both thromboembolism and known congenital hypercoagulable conditions.
- 2.1.2.12 Radioimmunotherapy within 2 years prior to enrollment in the study.

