# 3.2.3 Drug administration scheme

	Cycle 1 only								
Time point	d-2	d1	d2	d3	d4	d5	d6	d7	d8
Treatments									
Rituximab/Ruxience 375 mg/m 	X								
Moxetumomab pasudotox-tdfk 30-40 mcg/kg		X		X		X			
Hydration			•		•		•	•	•
H 2 O (6 L)		X	X	X	X	X	X	X	X
Pre-hydration-5% Dextrose 0.45% NaCl (1 L) 		X		X		X			
Post-hydration-5% Dextrose 0.45% NaCl (1 L) 		X		X		X			
Premedications	'		•		•	•		'	•
Dexamethasone (12 mg)	X								
Acetaminophen (650 mg)	X 	X 		X 		X 			
Diphenhydramine (25-50 mg) 	X								
Famotidine (20-40 mg)	X	X 		X 		X 			
Daily medication									
Aspirin (81 mg) 		X	X	X	X	X	X	X	X

				Cycle	s 2-8			
Time point	d1	d2	d3	d4	d5	d6	d7	d8
Rituximab/Ruxience	X							
Moxetumomab pasudotox-tdfk	X		X		X			
Hydration								
H 2 O (6 L)	X	X	X	X	X	X	X	X
Pre-hydration-5% Dextrose 0.45% NaCl (1 L) 	X		X		X			
Post-hydration-5% Dextrose 0.45% NaCl (1 L) 	X		X		X			
Premedications							•	
Dexamethasone (12 mg)	X 							
Acetaminophen (650 mg)	$X^{1,5}$		X 		X 			
Diphenhydramine (25-50 mg) 	X 							
Famotidine (20 – 40 mg)	X 		X 		X 			
Daily medication	•							
Aspirin (81 mg) 	X	X	X	X	X	X	X	X

Version Date: 04/16/2025

-  To be given 30-90 minutes prior to every moxetumomab pasudotox-tdfk infusion and recommended every 6 hours x 4 after the end of infusion.
-  0.9% Sodium Chloride Injection may be substituted for 5% Dextrose 0.45%NaCl.
- Only if platelet counts  $\geq 100 \times 10^9/L$
-  Administer 0.5-2 hours before rituximab/Ruxience. If participant has previous reaction to rituximab/Ruxience, give 12mg. If participant tolerates rituximab/Ruxience without problems, may hold at discretion of provider.
- Premedications are given prior to rituximab/Ruxience on day 1.
- Famotidine 20 40 mg to be given 30-90 minutes prior to every moxetumomab pasudotox-tdfk infusion and is recommended every 12 hours x 2 after the end of infusion
- May be given prior to moxetumomab pasudotox-tdfk at discretion of PI

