## 4 CONCOMITANT MEDICATIONS/MEASURES

- Prophylactic measures for renal toxicity, hypvolemia, rituximab/Ruxience toxicity and nausea and vomiting will be administered as described in Section 3.1.4.
- Febrile Neutropenia, which is common in participants before responding to treatment, may require empiric antibiotics, either as an inpatient or outpatient. Hematopoietic growth factors may be used if clinically indicated, for example, if grade 3-4 neutropenia is associated with suspected infection. Fever is also common with rituximab/Ruxience and may be treated symptomatically and with interrupting or with decreasing the infusion rate.
- Symptomatic anemia should be treated with appropriate red blood cell support. Transfusion is generally recommended if the hemoglobin falls below 7g/dL. Platelets are generally given when the platelet count is < 8,000/mm^3 or when there is bleeding.
- Participants receiving rituximab/Ruxience, particularly those with high concentrations of circulating malignant cells, commonly have infusional toxicities including fever, chills, nausea and vomiting, dyspnea, hypotension, and palpitations. Infusional reactions with rituximab/Ruxience have been observed in HCL as well as other malignancies and are best managed by slowing or interrupting the rate of infusion.
- Additional toxicities that may arise will be managed per current evidence-based practice guidelines in consultation with a medically responsible investigator if available.
- Concurrent chemotherapy, radiotherapy, immunotherapy, and biologic therapies for treatment of HCL during the study are not permitted.
- Use of steroids is not routinely recommended to prevent CLS or fever from moxetumomab pasudotox-tdfk; however, secondary prophylaxis for infusion-related reactions with dexamethasone IV or oral may be administered at the investigator's discretion.
- Participants will be informed that NSAIDs (except aspirin) should not be taken from the first dose of the cycle through 7 days after the last dose of the cycle.

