# **Step 8: Post-infusion Medications**

- Administer post-infusion medications.
- Intravenously administer 1 L of isotonic solution (e.g. 5% Dextrose Injection, USP and 0.45% or 0.9% Sodium Chloride Injection, USP) over 2 to 4 hours after each LUMOXITI infusion. Administer 0.5 L to participants under 50 kg.
- Consider oral antihistamines and acetaminophen for up to 24 hours following LUMOXITI infusions.
- Consider oral corticosteroid (e.g. 4 mg dexamethasone) to manage nausea and vomiting.
- Maintain adequate oral fluid intake.
- Advise all participants to adequately hydrate with up to 6 L (twelve 8-oz glasses) of oral fluids (e.g. water, milk, or juice) per 24 hours on Days 1 through 8 of each 28-day treatment cycle. In participants under 50 kg, up to 2 L (eight 8-oz glasses) per 24-hour period is recommended.
- Consider low-dose aspirin on Days 1 through 8 of each 28-day treatment cycle.

Note: This Healthcare Provider Instructions for Use has been approved by the U.S. Food and Drug Administration.

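### Sections 3.2.1 and 3.2.3 direct aspirin on platelet count alone, with no exception for bleeding or for the anticoagulated participants whom 2.1.1.7 admits

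*Combined protocol and SAP*

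**What the plan says.** Section 3.2.1 prescribes aspirin, together with fluids, to protect renal function. The instruction is mandatory: "Participants will receive low-dose aspirin orally (81 mg daily or local standard dose) on Days 1-8 of those cycles with platelet counts" reach 100 × 10^9/L or more. The only stated reason to interrupt it is also a platelet count: "Aspirin will be held on days where the platelet count is below 75" × 10^9/L.

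The drug administration scheme in 3.2.3 marks aspirin 81 mg on every day from d1 to d8, in cycle 1 and in cycles 2-8. Footnote 3, attached to the aspirin row, begins "Only if platelet counts" and sets the same threshold of 100. It contains no other condition.

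Inclusion criterion 2.1.1.7 sets separate coagulation limits for participants who are already anticoagulated: "If on warfarin, PT/INR < 3.5x ULN; If on any other anticoagulation, Prothrombin time (PT) < 2.5x baseline". The nearest exclusion, 2.1.2.11, covers "Participants with a history of both thromboembolism and known congenital hypercoagulable conditions", so both features must be present.

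Section 4 deals with aspirin only as an exemption from the NSAID restriction: "Participants will be informed that NSAIDs (except aspirin) should not be taken from the first dose of the cycle". It does not mention anticoagulants.

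Appendix C, Step 8, which reproduces the product's instructions for use, says: "Consider low-dose aspirin on Days 1 through 8 of each 28-day treatment cycle".

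**The concern.** The eligibility criteria show that anticoagulated participants were foreseen, since they have their own laboratory limits. The aspirin instruction was then written as if no such participant could be enrolled. An investigator who follows 3.2.1 and 3.2.3 literally gives an antiplatelet drug on top of an anticoagulant, with nothing in the text prompting a benefit-risk judgement. An investigator who sensibly withholds aspirin departs from the written protocol, and Section 8.7 defines any non-compliance with the protocol as a deviation to be documented.

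What is at stake is an avoidable bleeding hazard for a subset of participants. The point concerns safety and drafting. It does not touch sample size, power, type I error or the analysis of the primary endpoint.

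**Working it through.** The plan states no figure on this point, so the check sets the provisions side by side.

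**1. Can an anticoagulated participant enroll?** Yes. Criterion 2.1.1.7 admits a participant on warfarin with PT/INR below 3.5 × ULN, or on another anticoagulant with PT below 2.5 × baseline. No exclusion bars anticoagulant use as such. Because 2.1.2.11 needs both thromboembolism and a known congenital hypercoagulable condition, past thromboembolism alone does not exclude.

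The documents give no ULN for INR. If it is assumed to be 1.1 to 1.2, the warfarin limit is 3.5 × 1.1 = 3.85 to 3.5 × 1.2 = 4.20. This is the outer limit at entry, not an expected value while aspirin is taken.

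**2. Can that participant meet the aspirin condition?** Yes. Platelets below 100/nL are only one of five alternative treatment indications in 2.1.1.2, so a participant can enter at 100 or above. Complete remission (CR) ordinarily requires platelets of at least 100,000/mm³ (6.4.2), which equals 100 × 10^9/L. Section 3.1 allows up to 4 further cycles after CR without minimal residual disease, within a maximum of 8. Responders will therefore usually qualify.

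**3. What does the text direct?**

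| Situation | 3.2.1 | 3.2.3 |
|---|---|---|
| Platelets ≥100 at cycle start, no anticoagulant | Give | Give |
| Platelets ≥100 at cycle start, on an anticoagulant | Give | Give |
| Platelets <100 at cycle start | Do not start | Do not give |
| Platelets <75 on a day within the cycle | Hold | Footnote does not mention 75 |
| Active bleeding, platelets ≥100 | No exception | No exception |

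The second and last rows are the gap. Both trial-specific sections direct aspirin there, and neither Section 4 nor the exclusion criteria change that.

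**4. Is discretion implied?** The drafting suggests not. In 3.2.3, footnote 4 lets the provider hold dexamethasone and footnote 7 leaves diphenhydramine before moxetumomab to the PI. In 3.2.1, Pneumocystis and viral prophylaxis are to be considered rather than given. The aspirin sentence contains no such language.

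**5. Exposure fixed by the schedule.** Days 1-8 give 8 aspirin days per qualifying cycle:
- one qualifying cycle: 1 × 8 = 8 days;
- all eight cycles given and qualifying: 8 × 8 = 64 days, the maximum.

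These figures restate the schedule and do not measure harm. Turning them into a bleeding risk would need the proportion of participants on anticoagulants and a bleeding rate with and without aspirin. The documents give none of these.

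**The case against.** The best defence is that aspirin is a deliberate safety measure. HUS occurred in 8.8% of participants in the phase 3 trial (1.2.1) and requires removal from therapy (3.6.1). Giving aspirin by default or withholding it by default is a clinical trade-off, and the documents quantify neither side. Safeguards also exist. Aspirin is not started below 100 and is held below 75. Platelets are checked before every infusion, PT/INR is scheduled pre-cycle and on day 8, and concomitant medications are reviewed at every visit. The PI may also stop study treatment in the participant's interest.

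Much of this stands. It argues against banning aspirin, and it limits how much weight the point can carry. It does not close the gap: no scheduled check is tied to an aspirin decision for an anticoagulated participant, and the PI's power in 3.6.1 is to stop study treatment, not to omit aspirin.

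Three stronger readings are tempting, and the documents do not support them.

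- **The platelet rules conflict at 75-99.** A reader might infer this when a count falls into that band during a cycle that began at 100 or above, by applying footnote 3 day by day. The footnote does not say it applies daily, and it sits on the aspirin row label, whereas footnotes 1, 4, 5 and 6 sit on individual day cells. It fits a per-cycle start rule at 100 alongside the per-day hold rule at 75 in 3.2.1. Nor should doses given at 75-99 be counted as avoidable harm, since the fix below keeps both thresholds.
- **Appendix C contradicts the body.** Section 3.2.1 does say "Please refer to Appendix C for information related to moxetumomab pasudotox-tdfk administration and preparation". But the appendix identifies itself as FDA-approved instructions for use, and its general advice to consider aspirin is compatible with a protocol that has considered it and set a platelet rule.
- **The trial's safety endpoint is affected.** Nothing in the documents shows this. Section 3.1.4 reports no DLT among the first 12 participants.

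**Conclusion.** The point holds as a gap in a mandatory instruction. Anticoagulated participants are expressly eligible, aspirin is directed for them whenever platelets qualify, and no provision makes an exception for anticoagulation or bleeding. The conclusion rests on the current text of 2.1.1.7, 2.1.2.11, 3.2.1, 3.2.3 and Section 4, and needs no numerical assumption.

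The size of the bleeding risk is unknown and cannot be bounded from the documents. If no anticoagulated participant enrolls, the anticoagulant part of the gap has no practical consequence. The 75-99 band and the wording of Appendix C are matters of editorial clarity only. The change is worth making because it removes an avoidable hazard at very little cost.

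**What to change.** Add to 3.2.1, after the platelet rules: *For participants on warfarin or another anticoagulant, give aspirin only if the investigator documents that the expected renal benefit outweighs the bleeding risk; do not give during active bleeding.* Leave the thresholds of 100 and 75 unchanged.

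Have footnote 3 in 3.2.3 refer to 3.2.1 for the platelet, anticoagulant and bleeding rules. As an editorial change, add to Appendix C, Step 8 that aspirin in this trial follows 3.2.1.

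The cost is a wording amendment and one documented decision for each anticoagulated participant. No test or visit is added, because the platelet, PT/INR and medication checks are already scheduled. The downside is that some anticoagulated participants may forgo aspirin as renal prophylaxis; their intravenous and oral hydration would continue.
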